7.1. Operational Procedures

The randomization code (treatment assignment) will be stored in the Lilly interactive web response system (IWRS) and will not be accessible to the blinded Lilly study team, except for those pre-specified in the unblinding plan to be unblinded, until the final database lock (DBL). Members from the SAC, AC, and the study global patient safety (GPS) scientist may be unblinded to data prior to the DBL. The SAC, composed of Lilly unblinded statistics personnel, PK/PD scientists and the PK/PD analysts (for efficacy/safety interim analysis only) will form a separate team from the Lilly blinded team. The SAC will obtain the randomization code from the unblinded inVentiv data movement group in order to generate unblinded TFLs for the AC. Membership is listed in [Table GBGJ.5](#) for each of the groups mentioned above.

More specifically, the inVentiv data movement group will load CRF data, clinical laboratory results, ECG, and IWRS data into the designed blinded and unblinded locations. The blinded version of the data will then be provided to the blinded Lilly study team. The unblinded data will be provided to the SAC. The inVentiv data movement group is not blinded, but is not involved in study-level activities.

Table GBGJ.5. Study H9X-MC-GBGJ Group Name and Membership

Group Name	Group Members
Blinded Lilly Study Team	Lilly clinical study team personnel who work on the study and have direct site contact including the clinical research physician, clinical trial manager, data sciences and solutions, global patient safety personnel, and study monitors, etc., and non site direct contact regulatory scientist, statistician(s). However, per Lilly procedure, for patient safety, the study GPS scientist will be unblinded to SAE patient level data for patient safety.
Blinded Lilly statistics group	Lilly statisticians and statistical analyst(s)
Statistical Analysis Center (Unblinded)	Lilly statisticians and statistical analyst(s)
Unblinded PK/PD team scientists (part of the SAC)	Lilly study team pharmacokinetic/pharmacodynamics (PK/PD) scientists and analyst(s), etc.
Assessment Committee	Lilly Physicians, Statisticians, and GPS personnel external to the study team
inVentiv data movement group	inVentiv data movement representative
The program senior management	Lilly dulaglutide senior medical director or above

Abbreviations: GPS = global patient safety; PD = pharmacodynamics; PK = pharmacokinetics; SAE = significant adverse events.

Periodically throughout the trial until the DBL, blinded data will be transferred by inVentiv data movement per the data transfer plan to the blinded Lilly study team members including the blinded Lilly statistics group for the purpose of preparing Study Data Tabulation Model (SDTM) and Analysis Data Model (ADaM) dataset, AC reports, trial level safety review reports, blinded AC reviews, TFL reviews, and CSR preparation. To minimize bias during statistical planning and data review, these transfers will be provided under the guidelines described in the following sections.

By setting up appropriate access privileges, the Lilly system will only allow unblinded personnel (unblinded statistician and/or programmers) to access data that contains unblinding information.

7.2. Site Level Unblinding

The procedure for site personnel to unblind an individual patient's treatment assignment for an emergency is described in the protocol Section 7.3. Emergency unblinding for adverse events may be performed by accessing the IWRS at the site level. When an IWRS Clinical Trial Study Management System (CT-SMS) is used to unblind a patient's treatment assignment, the computer application will maintain the date, reason for unblinding, and the identification of the person unblinding the treatment assignment. All calls resulting in an unblinding event are recorded and reported by the IWRS.

The site monitor is responsible for verifying compliance with the blinding procedures at the investigative site and verifying that access to the patients' treatment assignments remains restricted from the investigator and site personnel in direct contact with patients.

The investigator and site personnel are instructed to make every attempt to contact Lilly personnel when a patient's treatment assignment is unblinded at the site. The affiliate personnel document the unblinding records and inform the designated study team member, CTM, who documents the overall unblinding records for the entire study. The documentation is filed in the study files. A final Study Unblinding Summary will be prepared at the end of the study (at the study closeout).

7.3. Trial Level Safety Reviews

Periodic Trial Level Safety Review (TLSR) summaries and listings will be produced by the blinded Lilly statistics group and delivered to the blinded Lilly study teams per TLSR plan. These summaries will be blinded until after the DBL. They will contain neither randomization assignments nor post randomization primary endpoint HbA1c, dose information, or PK data with the potential to unblind. Blinding flags will be created in the central laboratory database, based upon the Alert and Blinding Criteria document maintained by the Clinical Laboratory Operations (CLO) group. These flags will blind specific report data to the site and investigators. Data transferred to and exported from the clinical laboratory results will not be blinded to the Lilly team or to the data management of third party organization performing the labs.

The complete list of TLSR variables include overall AEs, serious adverse events (SAEs), TEAEs AEs of special interest, laboratory data, vital signs, ECG, discontinuations, concomitant medications, and historical/pre-existing medical conditions.

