**Clinical Laboratory Tests**

Abbreviations: CKD-EPI = Chronic Kidney Disease-Epidemiology; CK-MB = creatine kinase-MB; EDTA = ethylenediaminetetraacetic acid; eGFR = estimated glomerular filtration rate; GLP-1 = glucagon-like peptide-1; HbA1c = hemoglobin A1c; HDL = high density lipoprotein cholesterol; LDL = low density lipoprotein cholesterol; PK = pharmacokinetics; RBC = red blood cells; VLDL = very low density lipoprotein cholesterol; WBC = white blood cells.

- a All tests will be performed by a Lilly-designated central laboratory, unless otherwise noted.
- b Urinary albumin and creatinine are measured; the ratio is calculated.
- c Remaining P800 plasma from glucagon collection for non-pharmacogenomic biomarker sample.
- d CK-MB is to be assayed if the creatine kinase result is >1000 IU/L.
- e For those visits when fasting glucose is required, glucose will not be included in the chemistry panel.
- f CKD-EPI equation described in Levey et al. 2009.
- g This value will be calculated. If triglycerides >400 ng/mL, then direct LDL will be assayed.
- h Serum pregnancy test will be performed by central laboratory at Visit 1 for women of childbearing potential; urine pregnancy test will be performed at the site at Visit 3 for women of childbearing potential. Additional pregnancy tests may be performed at the investigator's discretion during the study.

---

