#### ***Appendix 3.2.1. Data Capture System***

An electronic data capture system will be used in this study. The sites will maintain a separate source for the data entered by the site into the sponsor-provided electronic data capture system.

Case report form data will be encoded and stored in a clinical trial database. Data managed by a central vendor, such as laboratory test data or ECG data, will be stored electronically in the central vendor's database system. Data will subsequently be transferred from the central vendor to the Lilly data warehouse.

Any data for which paper documentation provided by the patient will serve as the source document will be identified and documented by each site in that site's study file. Paper documentation provided by the patient will include diaries and dosing records.

Data from complaint forms submitted to Lilly will be encoded and stored in the global product complaint management system.

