7.4. Assessment Committee Reports

The blinded Lilly study team will remain blinded to randomization assignments and potentially unblinding results until after the DBL.

The SAC statistician is responsible for authorizing the access of Lilly personnel to unblinded data. Every attempt should be made to contact the statistician and document the authorization before access is given to unblinded data. A designated Interactive Web Response System (IWRS) representative, inVentiv data movement team or the replacement or their designee, will provide all data transfers to the Lilly statistics group based on the data transfer plan.

The study project statistician will be responsible for keeping a running log of individuals given access to any unblinded study data. This log will include the person's name, title, date of unblinding, level of unblinding (that is, group or patient), and purpose of unblinding. This record will be stored in a secure area and will be stored in eTFM via the study CTM after DBL.

Two types of interim analyses will be performed for this study:

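### SAP 7.3 says laboratory transfers are not blinded to the sponsor team; as worded this covers post-randomization HbA1c and conflicts with SAP 7.1, 7.4 and 7.5.2

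*SAP*

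**What the plan says.** SAP 7.3 describes periodic safety-review summaries, produced by the blinded statistics group for the blinded study teams. Of these summaries it says: "They will contain neither randomization assignments nor post randomization primary endpoint HbA1c, dose information, or PK data with the potential to unblind". It then introduces blinding flags in the central laboratory database and gives their reach: "These flags will blind specific report data to the site and investigators". The next sentence reads: "Data transferred to and exported from the clinical laboratory results will not be blinded to the Lilly team", and goes on to say the same of the data management staff of the third-party laboratory organization.

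Elsewhere the SAP sets a different rule for the blinded team. In 7.1 a contracted data movement group is to "load CRF data, clinical laboratory results, ECG, and IWRS data into the designed blinded and unblinded locations", and "The blinded version of the data will then be provided to the blinded Lilly study team". The end of 7.1 adds that system privileges restrict unblinding data to unblinded staff. SAP 7.4 states: "The blinded Lilly study team will remain blinded to randomization assignments and potentially unblinding results until after the DBL". SAP 7.5.2 places transfers with unblinded values for all laboratory parameters after the final lock.

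**The concern.** SAP 7.3 protects the summaries but, as worded, not the source data from which they are made. A data manager who follows its transfer sentence would send post-randomization HbA1c by patient to people whom 7.1 and 7.4 describe as blinded. The laboratory flags would not stop this, because they are aimed at sites and investigators.

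It matters because some analysis choices stay open until lock:

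- SAP 6.15 lets the study team classify further deviations as important at a later stage. It also uses a file kept by the clinical trial manager to help define the per-protocol population, and Table GBGJ.5 lists that manager in the blinded team.
- SAP 6.6 leaves the final per-protocol criteria to be documented in the trial master file.
- SAP 6.3 allows imputation rules to be added or changed without an SAP revision.

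Such choices are credible when those making them have not seen the outcome by patient.

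**Working it through.** The plan gives no figure on this point. The check is a comparison of the text, followed by one calculation to size the exposure.

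**Step 1. Does the transfer sentence reach HbA1c?** It does not name HbA1c, so this is an inference. Protocol Appendix 2 lists HbA1c among the clinical laboratory tests, with the footnote "All tests will be performed by a Lilly-designated central laboratory, unless otherwise noted". Protocol Appendix 3.2.1 says of data held by central vendors, including laboratory data: "Data will subsequently be transferred from the central vendor to the Lilly data warehouse". The Schedule of Activities has HbA1c drawn after randomization at Weeks 6, 10, 18 and 22 and at early termination. Nothing in 7.3 removes any of these values from the transfers; the HbA1c exclusion applies to the summaries only.

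**Step 2. Can the rules be followed together?**

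- SAP 7.3: laboratory transfers are open to the sponsor team, with no exception by analyte or subgroup.
- SAP 7.1: laboratory results are split between two locations, and the blinded team is served from the blinded one.
- SAP 7.4: potentially unblinding results are withheld from the blinded team until lock.
- SAP 7.5.2: unblinded values for all laboratory parameters follow lock, which implies that some are masked before it.
- Protocol 10.3.7.1, which is narrower: information from the PK/PD work that may unblind is kept from the blinded team until lock.

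The first rule is compatible with the others only if the sponsor team in 7.3 means unblinded staff, or if HbA1c is not potentially unblinding. The SAP states neither. By withholding HbA1c from the summaries, 7.3 itself treats the value as one the blinded team should not see.

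**Step 3. How much does one patient's HbA1c change reveal?** Inputs from Protocol 10.1 and SAP 5.2: a difference of 1.0 percentage point for each dulaglutide dose versus placebo, and SD 1.2. These refer to change from baseline. With normal changes and a common SD, the probability that a random dulaglutide patient shows a larger fall than a random placebo patient is

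AUC = Φ(δ / (SD × √2)).

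- δ = 1.0: Φ(1.0 / 1.697) = Φ(0.589) = 0.72
- δ = 0.5 (assumed): Φ(0.295) = 0.62
- δ = 1.5 (assumed): Φ(0.884) = 0.81

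The same information can be put as the probability that a patient is on dulaglutide. Randomization is 1:1:1:1, so the prior odds are 3:1 (probability 0.75). Assume a mean change of 0 on placebo and −1.0 on each dulaglutide dose. For an observed change y, the likelihood ratio is exp((−2y − 1) / (2 × 1.44)).

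- y = 0: ratio 0.71, odds 2.12, probability 0.68
- y = −1: ratio 1.42, odds 4.25, probability 0.81
- y = −2: ratio 2.83, odds 8.50, probability 0.89

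The change shifts the probability from 0.75 but does not settle any patient's assignment.

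**The case against.** The strongest defence is that the transfer sentence was meant more narrowly. It follows directly on the flags that mask site reports, so it may say only that those flags do not carry over into vendor exports. The group it names is not one of the groups in Table GBGJ.5, which separates the blinded study team, the blinded statistics group and the unblinded Statistical Analysis Center. On this view the split in 7.1, the access privileges and the data transfer plan act after the export and keep HbA1c from the blinded team. The transfer plan and the laboratory's blinding-criteria document, which could settle the matter, are not part of the protocol or SAP.

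This is a possible reading, and it is why the point stays at inconsistent rules. It does not remove the conflict. SAP 7.3 is about deliveries to the blinded teams, and 7.1 says that transfers to them follow the guidelines in the later sections, of which 7.3 is one. Nothing in the SAP states the narrower meaning.

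A second objection also has force: the primary analysis leaves little room for influence. SAP 6.11.1 fixes it as an MMRM in the ITT population with post-rescue data censored, and SAP 6.1 uses no imputation by default. The per-protocol analysis is a robustness check under SAP 6.11.2.1, and most of its exclusions are already listed in 6.15. SAP 6.3 does not say who may change imputation rules, so the documents do not establish that one team makes all the open choices. The blinded team also sees adverse events, vital signs and ECGs, so masking HbA1c would not remove every indirect clue.

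**Conclusion.** The conflict is real and should be corrected. As worded, SAP 7.3 opens post-randomization HbA1c by patient to the sponsor team, while SAP 7.1, 7.4 and 7.5.2 keep such results from the blinded team until lock. The conclusion rests on two readings: that an unqualified statement about laboratory transfers includes HbA1c, and that the team it names includes blinded members.

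The size is moderate. The AUC of 0.72 (0.62 to 0.81 over the assumed differences) assumes normal changes with a common SD. It applies to change from baseline, so the reader of the data would need both values; it does not describe a single HbA1c result.

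A reader might infer that the blinded team did receive HbA1c, that the trial was unblinded, or that the primary result is compromised. The documents support none of these. SAP 7.1 keeps treatment codes restricted, the primary analysis is prespecified, and HbA1c change does not identify an individual's arm. What is at stake is mainly the credibility of the supportive per-protocol analysis and of any imputation rules set before lock.

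**What to change.** Correct the SAP 7.3 sentence to name, using the groups in Table GBGJ.5, who receives unmasked laboratory data. State that until database lock post-randomization HbA1c goes only to the unblinded location used by the Statistical Analysis Center, together with any other analyte the sponsor judges potentially unblinding, such as fasting glucose. Bring the data transfer plan into line.

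Drug concentrations and antibody data need no new rule here. Protocol 9.5 already withholds unblinding concentration data from blinded personnel, and SAP 7.5.2 has immunogenicity data arriving after lock.

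The cost is modest, since separate blinded and unblinded locations already exist, but it is more than a change of wording. The transfer specification must change. Queries on masked analytes before lock must be handled by a named unblinded person or by the laboratory vendor. The data movement group cannot simply take them on, because SAP 7.1 places it outside study-level activities.

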7.4. Assessment Committee Reports

The blinded Lilly study team will remain blinded to randomization assignments and potentially unblinding results until after the DBL.

The SAC statistician is responsible for authorizing the access of Lilly personnel to unblinded data. Every attempt should be made to contact the statistician and document the authorization before access is given to unblinded data. A designated Interactive Web Response System (IWRS) representative, inVentiv data movement team or the replacement or their designee, will provide all data transfers to the Lilly statistics group based on the data transfer plan.

The study project statistician will be responsible for keeping a running log of individuals given access to any unblinded study data. This log will include the person's name, title, date of unblinding, level of unblinding (that is, group or patient), and purpose of unblinding. This record will be stored in a secure area and will be stored in eTFM via the study CTM after DBL.

Two types of interim analyses will be performed for this study:

7.4.1. Safety Only Reports

There are at least 3 unblinded safety only reviews. The following personnel will be unblinded to the safety data (efficacy measures will NOT be unblinded), in order to perform the safety data analysis, prepare the AC safety reports, and review/discuss the safety results:

- The AC (determined in AC Charter)
- Internal SAC (Lilly study personnel)
 - Computational Statisticians
- Others: No, but can be added upon AC Chair's request

7.4.2. Efficacy/Safety Interim Report

7.4.2.1. Model Development

For the interim analysis of efficacy, safety and pharmacokinetics, the following personnel will be unblinded to the pharmacokinetics related data about 4 to 6 weeks after approximately 80 subjects complete 18 weeks of treatment in order to develop the PK/PD modeling and/or TFLs:

- Internal SAC (Lilly study personnel)
 - Computational Statisticians
- Internal Pharmacokinetic Analysis Group (Lilly study personnel, part of the SAC)
 - Pharmacokineticist and Pharmacokinetics Analysts

7.4.2.2. Reports Delivery

The following personnel will be unblinded to the efficacy, safety, and pharmacokinetics data after approximately 120 subjects complete 18-week treatment, in order to perform data analysis, prepare the interim reports, review the results, and discuss business related matters:

- AC (determined in AC Charter)
- Internal SAC (Lilly personnel) or its delegate
 - Computational Statisticians
- Internal Pharmacokinetic Analysis Group (Lilly personnel, part of SAC) or its delegate
 - Pharmacokineticist and Pharmacokinetics Analysts
- Others: No, but can be added per the request from AC Chair and/or the program senior management

If PK reports need more time to be generated, this interim review can be proceeded without PK data. A subsequent PK results review can be formed later after the results are available.

In addition, in order to perform the critical business development and the regulatory interactions, some personnel need to be unblinded to the related summary (group) level data, and possibly limited patient-level data after the interim safety/efficacy analysis. This unblinding requires

approval from AC and signature for Confidentiality Responsibilities Agreement. The SAC statistician should be informed by AC Chair for documentation purpose.

7.5. Clinical Study Report

Prior to the final DBL, SDTM/ADaM datasets and draft TFLs will be produced by blinded team members and delivered to the blinded Lilly study team to review as appropriate.

7.5.1. *Prelock Unblinding*

Lilly PK/PD scientists along with the SAC statistician(s) who generate the data for PK/PD scientists will access randomization codes prior to the final DBL. Lilly PK/PD scientists will obtain unblinding information about 1 to 2 months before the DBL in order to perform PK/PD model-based analysis if deemed necessary.

7.5.2. *End of Study Unblinding*

After the final DBL, all transfers of SDTM/ADaM files and TFLs to Lilly will be unblinded and will contain unblinded results for all laboratory parameters, PK data, and CRF data.

Immunogenicity data will be obtained about 1 or 2 months after the final DBL in a separate transfer without overwriting the already locked database.

8. References

Lachin JM. Fallacies of last observation carried forward analyses. *Clin Trials.* 2016;13(2):161-168.

American Diabetes Association Workgroup on Hypoglycemia. Defining and reporting hypoglycemia in diabetes: a report from the American Diabetes Association Workgroup on Hypoglycemia. *Diabetes Care.* 2005;28(5):1245-1249.

9. Appendices

Appendix 1. Analysis Windows for the Selected Parameters

In clinical trials, visits do not always occur as scheduled in the protocol, and a certain visit may actually occur closer to the protocol-specified time of a different scheduled visit. When there is interest in the effect of the drug over time, using the visit number for analysis may not provide the best representation of time. For that reason, analysis windows will be used to define ranges of days relative to the date of first dose in order to associate collected data with scheduled time points of interest. These analysis windows will be implemented in ADaM, and they will not be used to overwrite or change the actual visit number that was reported by the site. Furthermore, these analysis windows are separate from the allowable range of days in the protocol's schedule of events for visits; they are not intended to be provided to sites so that there is no confusion regarding the acceptable timing of patient visits.

There will be cases where a patient has more than 1 measurement in the same analysis window. If multiple measurements fall within the same window but were collected on different days, the measurement closest to the target time will be used. If multiple measurements within the same window are equidistant from the target, the earlier measurement will be used to be conservative with regard to the drug effect. If more than 1 measurement was collected on the same day for a patient, the last measurement on that day will be used for that patient because there may have been an error with the test itself that caused the investigator to repeat it on the same day.

Table APP1.1. Analysis Windows for the Selected Parameters

	Screening and Lead-in		Treatment Period										Safety Follow-up
	V1	V2	V3	V4	V5	V6	V7	V8	V9	V10	V11	V12	V801
Visit	V1	V2	V3	V4	V5	V6	V7	V8	V9	V10	V11	V12	V801
Week	-2	-1	0	2	4	6	7	8	9	10	14	18	22
Day	-14	-7	1	15	29	43	50	57	64	71	99	127	155
Vital signs, Height, Weight, BMI	(-∞, -4)	(-10, -4)	(-3, 1)	(2, 22)	(23, 36)	(37, A)	(A+1, 53)	(54, 60)	(61, 67)	(68, 85)	(86, 113)	(114, B)	(B+1, C)
ECG	(-∞, 1)					(2, A)		(A+1, 64)		(65, 99)		(100, B)	(B+1, C)
6-point SMPG, Lipids panel (fasting), c-peptide, fasting insulin			(-∞, 1)									(2, B)	
Chemistry panel, urinary analysis, ACR, eGFR, Hematology	(-∞, 1)											(2, B)	
HbA1c, fasting glucose	(-∞, -7)		(-6, 1)			(2, A)				(A+1, 99)		(100, B)	(B+1, C)
(p) amylase, lipase, Serum calcitonin	(-∞, -7)		(-6, 1)			(2, A)						(A+1, B)	(B+1, C)
Fasting plasma glucagon			(-∞, 1)			(2, A)						(A+1, B)	
Calcitonin	(-∞, -7)		(-6, 1)									(2, B)	
Immunogenicity			(-∞, 1)			(2, A)						(A+1, B)	(B+1, C)

Abbreviations: ACR = albumin/creatinine ratio; BMI = body mass index; ECG = electrocardiogram; eGFR = estimated glomerular filtration rate; HbA1c = hemoglobin A1c; SMPG = self-monitored plasma glucose; V = visit.

Windows represent the range of days, relative to the date of the first dose, associated with a particular time point.

Note: (day1, day2), are inclusive.

A, B, C: actual day on which each patient individually ends the titration phase, maintenance phase, or safety follow-up. If the actual day is missing, the planned day of 46, 141, and 158 will be used to represent the end of the titration phase, maintenance phase, or safety follow-up.

Day 1: The day of the first dosing date or the day of the randomization date if first dosing date is missing

* When creating windows for the baseline, use the last non-missing pre-first dosing value.

The above analysis windows will not be used for analysis of hypoglycemia or compliance over time.

Any other parameters not listed in this table will use the site or investigator reported visit measurement directly without applying the visit window.

Leo Document ID = fd7b28a3-2e71-452d-9516-82fbf127c4af

Approver: PPD

Approval Date & Time: 08-Dec-2016 20:45:48 GMT

Signature meaning: Approved

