**Treatment Arms and Duration:**

At Visit 3, patients will be randomized in a 1:1:1:1 ratio to weekly injections of dulaglutide 4.5 mg, 3.0 mg, or 1.5 mg, or placebo, in combination with stable doses of metformin. Within each of the investigational dulaglutide dose (3.0 mg and 4.5 mg) arms, patients will be randomly assigned in a 1:1 ratio to 1 of the dulaglutide dose titration algorithms (Algorithm 1 or Algorithm 2). Study participants will be treated for 18 weeks after randomization in a double-blind manner, followed by a 4-week safety evaluation.

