**Number of Patients:**

A total of approximately 300 patients (~75 patients per arm and ~38 per algorithm) will be randomized and approximately 240 are expected to complete the treatment period (~60 per arm and ~30 per algorithm) to show that each dulaglutide dose arm is superior to placebo with at least 90% power. This sample size calculation assumes a treatment difference of 1.0% in HbA1c reduction, standard deviation of 1.2%, and dropout rate of 20%. The screen failure rate is estimated as 30%. Approximately 429 patients will be screened.

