Patients who stop the study drug permanently will receive another glucose-lowering intervention (rescue) and will continue participating in the trial according to the protocol to collect all planned efficacy and safety measurements.

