## 10. Statistical Considerations

### 10.1. Sample Size Determination

Assuming a screen failure rate of 30%, approximately 429 patients will need to be screened to attain approximately 300 patients randomized to the 4 treatment arms in a 1:1:1:1 ratio for 4.5 mg, 3.0 mg, 1.5 mg dulaglutide, or placebo weekly (~75 patients per arm). For the investigational dulaglutide dose arms (4.5 mg and 3.0 mg), approximately 38 patients will be assigned to each titration algorithm (Algorithms 1 and 2). Assuming a 20% dropout, this will result in approximately 60 patients per arm and 30 patients per algorithm (in each of the investigational-dose dulaglutide arms) completing the study.

The aforementioned sample size provides  $\geq 90\%$  power to demonstrate superiority for the dulaglutide doses (4.5 mg, 3.0 mg, and 1.5 mg) to placebo with respect to HbA1c change from baseline to 18 weeks. This assumes a true glycemic effect difference of -1% HbA1c for each dulaglutide dose versus placebo, and a standard deviation (SD) of 1.2% with a 2-sided alpha of 0.05.

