6.11.2.2. Missing data imputation

If the conclusions differ among the four populations listed in Section 6.11.1 and Section 6.11.2.1, additional analyses may be further explored using selected pattern mixture models for missing data (Kenward and Rosenkranz 2011) in the ITT population regardless of rescue therapy or compliance to the study treatment. In this case, imputed 18-week HbA1c response for the missing data along with the non-missing 18-week data will be employed using an ANCOVA model by removing all visit related terms. The missing data will be imputed from the non-missing subjects who took rescue therapy or continued on the study but discontinued study medication. Depending on the missing data status, the non-missing data used for imputation may be altered from what is described in this section.

The tipping-point approach is like a progressive stress-test to assess how severe departures from missing at random (MAR) need to be in order to overturn conclusions from the primary analysis. In the dulaglutide arms, the imputed values will be replaced by the imputed value plus a shift parameter beginning from 0 with the increment of 0.05. Each value of the shift parameter will be tested sequentially until the value is reached at which the conclusion from the MMRM analysis is reversed. That value is the tipping point indicating that the conclusion under MAR is questionable if this shift parameter value is plausible. If implausible departures from MAR are required to change the results from statistically significant ($p \leq 0.05$) to not statistically significant ($p > 0.05$), the results will be said to be robust to the departure from MAR assumption and provide more confidence in the results obtained based on statistical methods with the MAR assumptions.

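### The Week 18 window for pancreatic enzymes and fasting glucagon opens the day after titration ends, so early-termination values from as early as Week 7 enter the MMRM as Week 18

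*SAP*

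**What the plan says.** SAP 6.1 defines a scheduled visit, for the parameters in Table APP1.1, by the analysis window and not by the visit number the site reports. The table has no separate rule for early-termination values. If several values on different days fall in one window, "the measurement closest to the target time will be used".

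The bounds A, B and C are the "actual day on which each patient individually ends the titration phase, maintenance phase, or safety follow-up"; Days 46, 141 and 158 replace them only when the actual day is missing. The Week 18 windows (target Day 127) are:

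- pancreatic amylase, lipase and fasting glucagon: A+1 to B
- HbA1c, fasting glucose and ECG: Day 100 to B
- weight and vital signs: Day 114 to B

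The Protocol Schedule of Activities allows 7 days either side of Visit 12 and draws enzymes and glucagon at the early-termination visit. SAP 6.13.4.3 analyses the log enzyme ratio to baseline by MMRM. It reports dose contrasts against placebo and 1.5 mg at Week 18, and a Week 18 versus Week 6 ratio within treatment. SAP 6.17 assigns glucagon to the MMRM.

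**The concern.** An enzyme or glucagon value taken at early termination soon after titration is analysed as if it had been observed at Week 18. On Day 47 a patient has had about one week at the final dose, against the 12 weekly maintenance doses planned (Protocol Table GBGJ.2). Protocol 8.2 has drug stopped before the early-termination visit, so the value may also be off drug.

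The MMRM would otherwise treat that patient's Week 18 value as missing and rely on the missing-at-random assumption. Under the present window the early value stands as an observed Week 18 response.

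The enzyme results are most exposed. Protocol 5.4 says enzymes are measured repeatedly to understand how they change at the two investigational doses, and the Week 18 versus Week 6 ratio is meant to describe the change over maintenance. Contamination may also differ by arm: Protocol 3.2 reports that 5 of 33 earlier patients on 3.0 mg or more stopped early for gastrointestinal events.

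**Working it through.** **Inputs.** 75 patients per arm, 20% dropout and 60 completers per arm (Protocol 10.1); Visit 6 on Day 43, Visit 12 on Day 127 plus or minus 7, Visit 801 on Day 155 (Schedule of Activities and Table APP1.1).

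**The plan's own figures.** 75 × 0.80 = 60 completers, so 15 dropouts per arm. Target day = 7 × 18 + 1 = 127. The Visit 12 window is Days 120 to 134. All agree with the documents.

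**How early Week 18 opens.** Enzymes and glucagon at the fallback: 46 + 1 = Day 47, and 127 − 47 = 80 days early. HbA1c: 127 − 100 = 27 days early. Weight: 127 − 114 = 13 days early.

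**Passing early-termination days through the table.** The labels are the same whether B is the early-termination day or 141.

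| Early-termination day | Enzymes, glucagon | HbA1c | Weight |
|---|---|---|---|
| 20 | Week 6 | Week 6 | Week 2 |
| 60 | Week 18 | Week 10 | Week 8 |
| 80 | Week 18 | Week 10 | Week 10 |
| 99 | Week 18 | Week 10 | Week 14 |
| 100 | Week 18 | Week 18 | Week 14 |
| 114 | Week 18 | Week 18 | Week 18 |

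The closest-to-target rule does not help, because a patient who has left has no later value to displace the early one.

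**How many values.** Assume the 15 dropouts are spread evenly over 126 days and all give a sample. Count those labelled Week 18 but taken before Day 120:

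- Visit 6 on Day 43, so Days 44 to 119: 76/126 × 15 = 9.0 per arm; share 9.0/(60 + 9.0) = 13%
- fallback A = 46, so Days 47 to 119: 73/126 × 15 = 8.7 per arm; share 8.7/(60 + 8.7) = 13%
- window opened at Day 100: 20/126 × 15 = 2.4 per arm; share 2.4/62.4 = 4%
- window opened at Day 114: 6/126 × 15 = 0.7 per arm; share 0.7/60.7 = 1%

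If only half of the 9 give a sample (assumed), the share is 4.5/64.5 = 7%.

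**Effect on the results.** If early values differ from true Week 18 values by d on the log scale, a simple Week 18 mean shifts by 0.13 × d at the upper figure. The documents do not give d, so no direction or size follows. Between arms the shift cancels as far as shares and d are alike. Within an arm, the Week 18 versus Week 6 contrast has nothing to cancel it: for a Day 47 value it compares measurements 47 − 43 = 4 days apart instead of 127 − 43 = 84.

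**The case against.** **In defence of the window.** A+1 separates titration from maintenance, and no enzyme or glucagon sample is scheduled between Visits 6 and 12. The window uses an observed value once and copies nothing forward, so it is not literally LOCF. SAP 6.1 rejects LOCF ANCOVA for efficacy endpoints only, and SAP 6.3 openly keeps LOCF for non-longitudinal variables and selected safety laboratory measures. Enzymes are a safety measure and glucagon is exploratory. The count assumes even dropout with every patient sampled, whereas Protocol 5.5 describes nausea and vomiting onset diminishing by 4 to 6 weeks, and early leavers would fall in the Week 6 window.

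All of this is fair, and it limits the size. It does not justify the label: these parameters are assigned to a by-visit MMRM, and a value 80 days before target does not describe Week 18.

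**HbA1c.** A reader might infer that Day 100 for HbA1c is equally wrong because weight opens at Day 114. The documents do not support that. Both follow a midpoint rule: HbA1c is not measured at Visit 11, so (71 + 127)/2 = 99; weight is, so (99 + 127)/2 = 113. Early-termination HbA1c before Day 100 goes to Week 10 or Week 6. About 2.4 values per arm remain, all within 27 days of target. Censoring post-rescue data also largely protects the primary analysis, since patients who stop drug permanently are to receive rescue. Opening at Day 114 would discard observed data as a matter of preference.

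**Day B.** A reader might also infer that B is the day drug stops, so that the Day 127 value of a patient who stops but stays is moved to follow-up. Protocol 8.1.1 says such patients "will continue participating in the trial according to the protocol to collect all planned efficacy and safety measurements". Against that inference:

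- Protocol 5.1 bounds maintenance by Visits 6 and 12.
- C ends a period without study drug, so it cannot be a drug-stop day.
- The fallbacks follow visits: 141 = (127 + 155)/2 and 158 = 155 + 3.
- A last-dose reading (Week 17, Day 120) would send completers' Day 127 values to follow-up too.
- SAP 6.11.2.2 relies on Week 18 values from these patients: "The missing data will be imputed from the non-missing subjects who took rescue therapy or continued on the study but discontinued study medication".

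With B as the Visit 12 day, or 141, nothing moves. What stands is that the SAP does not name the event, and Protocol 5.1 also describes maintenance as a period of dosing.

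**Conclusion.** The point holds for pancreatic amylase, lipase and fasting glucagon. As written, the SAP analyses early-termination values from as early as Week 7 as Week 18 in an MMRM, and for enzymes these feed the Week 18 dose contrasts and the Week 18 versus Week 6 contrast. The upper figure is about 9 values per arm, 13% of Week 18 values; it rests on the plan's 20% dropout and on the assumptions of even timing and full sampling. The resulting bias cannot be sized from the documents.

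The point does not extend to the HbA1c window or the primary analysis. Nor do the documents show that off-drug patients' Week 18 values would be moved to follow-up; the definition of B needs a clarifying sentence and no more.

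**What to change.** In Table APP1.1, open the Week 18 window for pancreatic amylase, lipase and fasting glucagon close to the target: at Day 100, as for HbA1c and ECG, or at Day 114, as for weight. Either bound contains the whole Visit 12 window. Leave values from A+1 up to the new bound unassigned in the MMRM; keep them in the listings and, for enzymes, in the maximum post-dose summaries. Leave HbA1c at Day 100.

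The enzyme row also names serum calcitonin, which has its own row with Week 18 opening on Day 2. The same edit should say which row governs.

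As a clarification, state that A, B and C are the actual Visit 6, Visit 12 and Visit 801 days whether or not study drug was stopped.

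The cost is SAP wording and a few early-termination values leaving the Week 18 MMRM: at the upper figures, 8.7 − 2.4 = 6.3 to 9.0 − 2.4 = 6.6 per arm with Day 100, or 8.7 − 0.7 = 8.0 to 9.0 − 0.7 = 8.3 with Day 114, and fewer if dropout is early. Those patients then count as missing at Week 18 under the SAP's missing-at-random assumption.
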